Endpoints	
Primary
 
 • 7-day Sleep efficiency, at baseline and endline • 12-day nocturnal mean glucose (using Continuous Glucose Monitors (CGM) during sleep), at baseline (0 weeks) and endline (12 weeks) 
Secondary
 
 • Endothelium-dependent vasodilation (measured by ultrasound image analysis as Flow-Mediated Dilation (FMD)), at baseline and endline. • 12-day daytime and 24-hour glucose metabolism (CGM outcomes, glycaemic variability, time in range). • 48hrs nocturnal, daytime and stress-related heart rate variability (measure of autonomic function; higher range the more autonomic function) • 12-week daytime and night-time continuous blood pressure (Aktiia blood pressure bracelet) • Blood parameters 
 ◦ Glucose control (fasting HbA1C, fasting glucose and insulin) ◦ Lipids • Body composition 
 ◦ weight and waist circumference ◦ % body fat and lean body mass (Tanita scales) • Visual Analogue Scale (VAS) assessments of satiety, included in 4-day diet diaries. • Urinary potassium and sodium • Urinary alkaloids (calystegines) 
Compliance
 
 • Urinary potassium and sodium • Dietary assessments 
 ◦ 24-hour recall (Wk 2, 4, 8) ◦ 4-day food diary (Wk 0, 6, 12) ◦ Self-reported adherence: checklist of evening meal
Main Inclusion Criteria	Participants will be healthy male or females, aged between 40-80 years who consume ≤4 fruits and vegetables a day (excluding potatoes), with a less favourable sleep efficiency score of <85%

Statistical Methodology and Analysis	
Differences between groups (minimized for age, gender, BMI) will be analysed using Linear mixed models for outcomes with 3 timepoints (urinary outcomes, dietary intake data), with change being the dependent factor, participant ID as random effect, treatment and season as fixed effects, and baseline outcome and BMI as covariates. Variables with 2 timepoints will be assessed with an ANCOVA regression model.
 
A 2 -sided P value <0.05 will be considered as showing statistical significance.
 
For more details of statistical analysis plan, see section 4.2.

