Compliance will be monitored by 24 h urinary potassium excretion, which is shown to recover 75% of potassium intake (39). These samples will be analysed by flame photometry (40). No other appropriate biomarkers of compliance are specific enough to monitor differences in the control and potato interventions in this study design. Additionally, sodium excretion will be analysed to indicate dietary sodium intake. This is a relevant indicator in our study as sodium intake could confound the results of this study.

Urinary creatinine will be used as one marker to distinguish between complete and incomplete 24 h urine collections (41), specifically the Knuiman et al creatinine excretion method (urinary creatinine [mmol/d] \times 113)/(21 \times body weight [kg]) (42), which has been shown to be the most sensitive and specific (43). Samples with a creatinine index <0.7 will be discarded as incomplete.

Additionally, self-reported missing samples (more than a few drops, as assessed by word of mouth and urine collection forms) and samples with a total volume <400 mL will be marked as incomplete, as outlined in the NHANES survey (44).

Midline urine samples will be analysed within a week of collection, to assess compliance.

Dietary Assessment

Dietary assessment evaluations will be built into the study design to evaluate and encourage compliance to treatments, including 4-d food records (WK 0, 6, 12), and 24h dietary recalls (WK 2, 4, 8) with the multipass method (45).

Additionally, self-reported compliance methods will be employed via an evening meal checklist in the data diaries provided to participants. This will determine the level of compliance (%) and may be used as stratum in analysis. $\geq 75\%$ of overall days exposed to the starch, as well as 75% of the days exposed in the final four weeks, will be counted as compliant. Any rates below 75% in either of these time periods, will be counted as non-compliant for ITT.

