3.8 Inclusion and exclusion criteria

- **Inclusion criteria**
 - Healthy adults
 - Aged 40-80 years old
 - Intake of ≤ 4 portions of fruits and vegetables (excluding potatoes) per day
 - Low sleep quality- $<85\%$ sleep efficiency score on the PSQI
 -
- **Exclusion criteria**
 - Shift workers and those with multiple jobs or carers who are required to wake through the night
 - Unwilling to refrain from dietary supplements
 - Unwilling to follow protocol and/or give informed consent
 - Diagnosed with Cardiovascular Disease (CVD), Type 2 Diabetes, Celiac disease, Insomnia, Sleep apnoea
 - Presence of gastrointestinal disorder
 - Users of drugs that are likely to alter gastrointestinal motility or nutrient absorption
 - History of substance abuse or alcoholism
 - Currently pregnant, planning pregnancy, breastfeeding or having had a baby 12-month prior
 - Weight change of $>3\text{kg}$ in preceding 2-months
 - $\text{BMI} <18.5\text{kg/m}^2$ or $> 35\text{kg/m}^2$,
 - Current smokers, or individuals who quit smoking in the last 6-months
 - Frequently consume wholemeal products (1-2 times per day, in the short screening FFQ)
 - Never consumed refined starchy staple, such as white pasta or rice (rarely or never, in the short screening FFQ)
 - High potato consumption (4-6 times per week, in the short screening FFQ)
 - High risk of obstructive sleep apnoea (answer yes to >3 questions, in STOP-Bang questionnaire)

V5.1 31/08/2025

NON-CTIMP randomised trial

Clinical Trials ref: NCT05994313

REC: HR/DP-22/23-35587

- Vegan
- Sleep-related medications, or medications that may interfere with sleep
- Fasting glucose >7mmol/l (finger prick test at baseline clinic)

Table 2. Event and Outcome matrix

Body composition (Tanita scales)	Researcher	Secondary outcome					✓						✓		
HRV (48-hours and acute response to stress)	Researcher	Secondary outcome					✓						✓		
Weight	Participant	Secondary outcome													✓
Blood pressure	(Automated via bracelet)	Secondary outcome												✓	
4-day food diary + appetite visual analogue scale	Participant Baseline and Endline: 24-hr before clinics Midline: taken at home and sample posted	Dietary data for quality indices/covariates PDI (uPDI, hPDI) aMED aHEI HFD					✓			✓			✓		

[figure not shown]

Figure 4. Flow diagram of RCT process.

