This follow-up session will be an overview and a chance for participants to ask outstanding questions. This will ensure that the study lead is happy that participants have suitable understanding of the process and are happy to continue with the process.

A summary of the training needs that will be addressed are written below:

Self-taken measurements include:

1. Body weight with home scales (Weekly, from wks.0 - 12)

Need to apply the following equipment alone:

1. Motion watch (7days)
2. Aktiia bracelet (7 days)
3. CGM (12 days)

Participants will be made aware that they are able to contact the study team at any time when they need. The contact details (study email and phone number) will be provided in the participant information guides they receive along with their equipment, as well as on email invitations.

4th contact: Clinic visit 1 (Wk 0), MRU at KCL. ~130 minutes.

The study team will have correspondence with participants to arrange a suitable date for their baseline clinic visit.

Participants will attend the MRU, 4th Floor, Franklin Wilkins Building, Kings College London and have the following procedures:

1. Urine samples collected (~0 mins)
2. Finger prick blood test (~10 minutes)
3. Blood pressure (~10 mins)
4. Fasted bloods (~20 mins)
5. Heart rate variability monitor fitted (ECG), to keep on for 48-hours (~10 mins)
6. Ultrasound imaging (~30 mins)
7. STROOP test (~15 mins)
8. Body composition and waist circumference (~10 mins)*
9. Questionnaires (ZOE FFQ) (~15 mins)
10. Dietary consultation (20 mins)***

*Optional break for a snack post measurements.

**Participants will then be instructed to start the dietary protocol after 48 hours after the baseline clinic, when participants' baseline HRV has been recorded.

***Participants will be required to attend a brief consultation with the associate nutritionist on the dietary intervention they have been assigned to. This will cover cooking methods, appropriate food items, and menu card run throughs. It will also provide an opportunity to problem-solve around identified conflicting commitments such as holidays or celebrations, where the participants may not be able to follow the intervention. Standardised advice on eating out will be given to all participants. General healthy eating advice will also be delivered, roughly in line with UK and US dietary guidelines.

5th contact: Dietary assessments for compliance

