1. Video/telephone call. 24-hour food recall, multipass method. ~30-60 mins. (Wks 2, 4, 8)

Participants will have 2 phone calls in weeks 4 and 8, to carry out a 24-hour food recall, a well-regarded measure of dietary intake (45). This will be conducted by an associate nutritionist, with experience of conducting these methods.

Participants will be contacted by the study lead or supervised delegate, to arrange a suitable time for these calls.

As the study is long-term (12 weeks) and free-living, we have built in these compliance checks to allow us to make suggestions to tailor the programme to the needs of the participants if necessary.

7th contact: Clinic visit 2 (Wk 11-12), MRU, KCL. 110 minutes

Participants will attend the MRU, 4th floor, Franklin Wilkins Building, Kings College London for their final engagement. And have the following procedures:

1. Urine samples collected (~0 mins)
2. Blood pressure (~10 mins)
3. Body composition and waist circumference (~10 mins)
4. Fasted bloods (~20 mins)
5. Ultrasound imaging (~30 mins)
6. Heart rate variability monitor fitted (ECG), to keep on for 48-hours (~10 mins)
7. STROOP test (~20 mins)
8. *Optional break for a snack ultrasound.*

Additional measurements made outside of the study visits:

- **4-day diet diaries:** participants will be asked to complete 4-day diet diaries during week 1, week 6 and week 12 of the diet intervention. The 4-day diet diaries are to be completed on non-consecutive days to reflect the intakes of 3 weekdays and 1 weekend day. It will also ask participants to record their satiety from their dinner, on day 1, using 100mm visual analogues scales, at 1-, 2- and 3-hours post meal.
- **Blood pressure** will be taken at home using an automated BP bracelet. Participants will need to put the bracelet on during the study run, and wear it throughout the study. As the bracelet is no waterproof, it will need to be taken off and reapplied after bathing/water activities. It will also need to charged every 25 days and initialized with an accompanying blood pressure cuff to calibrate it.
- **Weight** will be taken by the participant at home, using home weighing scales. Advice will be given on how to standardize these measurements to account for inter and intra variability. This measurement will be taken in the morning before food or drink on even hard flooring at monthly intervals (Table 2). Weighing scales will be provided to participants if they are not in possession of any.

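### Section 5.4 puts the first food diary and satiety VAS in week 1 of the diet, while the rest of the protocol says Week 0; if Section 5.4 is followed, the baseline is on treatment

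*Combined protocol and SAP*

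**What the plan says.** Four places bear on when the first diary is kept. The additional-measurements list in Section 5.4 (Schedule of Treatment) says that "participants will be asked to complete 4-day diet diaries during week 1, week 6 and week 12 of the diet intervention". The synopsis, under compliance, has "4-day food diary (Wk 0, 6, 12". Section 3.2, under dietary assessment, has "4-d food records (WK 0, 6, 12". Table 2 has a row for "4-day food diary + appetite visual analogue scale" with three ticks; its column headings are lost in the copy available.

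The satiety measure travels with the diary. The synopsis lists among the secondary endpoints "Visual Analogue Scale (VAS) assessments of satiety, included in 4-day diet diaries", and Section 5.4 ties it to dinner on the first diary day.

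The start of the diet is fixed relative to the baseline visit, "4th contact: Clinic visit 1 (Wk 0), MRU at KCL. ~130 minutes". That visit's procedure list ends with a consultation on the assigned diet, and "Participants will then be instructed to start the dietary protocol after 48 hours after the baseline clinic".

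Both descriptions of the analysis adjust for baseline. The synopsis puts dietary intake under a mixed model for change, with the baseline outcome as covariate. Section 4.2 lists only urinary measures as three-timepoint outcomes and sends everything else to ANCOVA with baseline as covariate. Neither text names the satiety VAS.

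**The concern.** Section 5.4 is the only text written as an instruction on when to fill in the diary. Taken at its word, the first diary records meals that already contain the assigned potato, rice or pasta, and the first VAS follows an assigned-starch dinner. If that record is then treated as baseline, the covariate carries part of the treatment effect, and adjusting for it subtracts that part from the estimate. At stake are a listed secondary endpoint, the dietary-intake comparisons and change in the diet-quality indices. Section 3.3 also names satiety and diet quality among the routes by which potatoes might lower nocturnal glucose, so a muted satiety result could be misread as evidence against that route.

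**Working it through.** **Step 1. The schedule, side by side.**

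| Source | First diary | Relation to diet start |
|---|---|---|
| Section 5.4, additional measurements | week 1 of the diet | after, wholly or mostly |
| Synopsis | Week 0 | baseline week |
| Section 3.2 | Week 0 | baseline week |
| Table 2, diary/VAS row | first tick in the same column position as the first ticks for body composition and HRV, both done at the Week 0 clinic | baseline timepoint |

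Section 5.4 is the outlier. None of the four says in terms that the diary must be finished before the diet begins.

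**Step 2. Could a week-1 diary still be pre-diet?** Section 5.4 asks for four non-consecutive days. Within seven days the only such set is days 1, 3, 5 and 7.

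- Week 1 counted from diet start: all four diary days and the VAS are on diet.
- Week 1 counted from the clinic day: the 48 hours cover days 1 and 2, so only diary day 1 precedes the diet. Its VAS could then be pre-diet, but three of the four diary days are not.

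**Step 3. Effect on the adjusted estimate.** The documents give no figure for diary or VAS outcomes, so there is no planned value to reproduce. Let δ be the true effect at follow-up, f the share of it already present in the first record, and b the within-arm slope of follow-up on that record (with equal SDs, b is the correlation).

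- ANCOVA on the follow-up value: δ − b·(fδ) = δ(1 − b·f).
- Change as outcome, same covariate: the slope becomes b − 1, so the coefficient is (δ − fδ) − (b − 1)fδ = δ(1 − b·f). The result is the same, so it does not matter which of the two model descriptions is used.

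The values of b and f below are assumptions. The share of δ retained is:

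| b | f = 0 | f = 0.5 | f = 1 |
|---|---|---|---|
| 0.3 | 1 | 1 − 0.15 = 0.85 | 0.70 |
| 0.5 | 1 | 1 − 0.25 = 0.75 | 0.50 |
| 0.7 | 1 | 1 − 0.35 = 0.65 | 0.30 |

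A simulation with 400,000 subjects per cell agrees. For b = 0.3, 0.5 and 0.7 it gave 0.998, 0.996 and 0.996 at f = 0; 0.859, 0.749 and 0.654 at f = 0.5; and 0.708, 0.500 and 0.298 at f = 1.

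**Step 4. Reach.** The sample size in Section 4.1 rests on nocturnal glucose and sleep efficiency, neither of which comes from the diary. Its 34 per arm for glucose reproduces: a two-sided t-test at 0.025 with difference 0.468, SD 0.61 and 80% power needs 33.6. Nothing here changes it.

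**The case against.** The strongest reply is that one line is being set against three. The synopsis, Section 3.2 and the tick positions in Table 2 all point to Week 0. The analysis text speaks only of baseline and never says that a week-1 diary would serve as one. Week labels are loose elsewhere too: Section 3.2 attaches week 2 to the dietary consultation that Section 5.4 holds at the Week 0 clinic. On the Week 0 schedule, with the diary completed before the diet, f = 0 and there is no bias. All of this stands, and it is why the attenuation can only be stated conditionally. It does not remove the contradiction, because the line that differs is the one participants would be asked to follow.

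A reader might infer several stronger things that the documents do not support:

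- *The baseline is on treatment as a settled fact.* Three places say otherwise.
- *The effect would vanish.* That needs an unadjusted change score with f = 1; both model descriptions adjust for baseline.
- *Adherence cannot be judged without a pre-diet diary.* Section 3.2 defines compliance from the evening-meal checklist kept during the diet. A food frequency questionnaire and baseline urinary potassium are also collected at Week 0. The questionnaire is not listed at the final visit, however, so it cannot stand in for the diary when measuring change.
- *The primary glucose analysis is contaminated through diet quality.* Section 3.3 mentions the diet-quality indices as covariates, but Section 4.2 does not include them in any model.

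**Conclusion.** The point holds as an internal contradiction with a conditional consequence. Section 5.4 puts the first diary and VAS in week 1 of the diet, so they fall wholly or mostly after the assigned starch has started; the synopsis, Section 3.2 and Table 2 put them at baseline. If the Section 5.4 timing is followed and the record is used as baseline, the adjusted estimates for satiety and dietary intake are shrunk to 1 − b·f of the truth. The illustrative ranges are 30% to 70% retained at f = 1 and 65% to 85% at f = 0.5. The actual loss cannot be fixed from the documents, and it is nil if either b or f is zero. For satiety there is a further assumption: that the VAS, measured three times but named in no model, is analysed with baseline adjustment under the catch-all in Section 4.2. The damage is confined to secondary and dietary outcomes.

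**What to change.** Three changes, best made before the analysis begins:

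1. Reconcile Section 5.4 with the synopsis, Section 3.2 and Table 2, so that the first diary and VAS are completed before the dietary consultation at clinic visit 1, and hence before diet start. Leave weeks 6 and 12 as they are.
2. Name the model for the satiety VAS as a three-timepoint outcome, and make the synopsis and Section 4.2 agree on dietary intake.
3. State that any first diary or VAS dated after diet start is not used as the baseline value or covariate for satiety, intake or diet-quality indices. Only the baseline value should be set aside. The participant stays in the intention-to-treat comparison, so the plan must say how a missing baseline is handled; otherwise a regression would drop that person by default.

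The first change costs one line in the schedule and participant guide. The diaries are already in the pack posted after consent, so no visit or measurement is added. The synopsis gives an estimated primary completion of May 2025, before this August 2025 version, so collection may already be over. The third change still works in that case, provided that diary dates and diet start dates were recorded. Its cost is the precision lost where the baseline cannot be used.

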5.6 Equipment overview

[figure not shown]
At home, at baseline and endline, participants will be wearing an Abbott's Freestyle Libre 3 for 14 days (A), a MotionWatch 8 for 7-days (B), a waterproof eMotion-Faros 180 for 3 days (C), and an Aktiia blood pressure bracelet for 14-weeks (D). Training will be given on how to apply A, B & C. D will be applied at the study visit.

Participants will take their own weight weekly throughout the study (with bathroom scales, which can be provided if they do not own any).

Participants will receive leaflets and/or videos on how to apply and use this equipment, entailing any contraindications or warnings of the study equipment (i.e. original models of Aktiia not being waterproof). In addition to this, all equipment will be discussed during the run-in 1:1 induction call,

where any questions can be asked, and the study team can check participants are comfortable and happy to proceed. Participants will also receive a copy of the manuals of each item via email, should they need to refer to it.

All study equipment will be returned to the study team upon finishing their participation.

5.7 Methods of engagement

Engagement strategy

As our methods are over a longer study period, we will implement the following methods to reduce study drop out and improve adherence:

- Introductory call to build rapport
- Video/telephone call through run-in induction
- Compliance measures: 24-hour food recalls and food diaries
- Email reminders of milestone events: Intervention start, clinic days, midline urine samples, when equipment has been sent.

5.8 Follow up Procedures

Not relevant for this study.

5.9 Laboratory Assessments

Fasting blood samples

The blood samples will be analysed at certified laboratory, Affinity Biomarker Laboratories, [name]. [name] will be the recipient of the samples ([contact]). This laboratory has been used before, so all necessary contracts between the laboratory and KCL have been established. Quotations for the analytes have been received and will be confirmed upon receiving favourable opinion from the board of ethics.

The analytes and the respective diagnostic tests are summarised below.

Analyte	Analysis method ⁽¹⁾
Full lipid profile	Cholesterol Clinical Chemistry Analyser: SIEMENS ADIVA 1800. Chemistry cholesterol method. (Cholesterol (CHOL-2) reagent catalogue number 10376501)
	HDL Clinical Chemistry Analyser: SIEMENS ADIVA 1800. Chemistry Direct HDL method. (Direct HDL (HDL) reagent catalogue number 07511947)
	LDL Clinical Chemistry Analyser: SIEMENS ADIVA 1800. Chemistry Direct LDL method. (Direct LDL reagent catalogue number 09796248)
	TAG Clinical Chemistry Analyser: SIEMENS ADIVA 1800. Chemistry Triglyceride method. (Triglyceride (TRIG-2) reagent catalogue number 10335892)
Serum potassium	Clinical Chemistry Analyser: SIEMENS ADIVA 1800. Indirect ion selective electrode (ISE). (ISE reagent catalogue number 06135445 (Potassium))
Plasma glucose	Clinical Chemistry Analyser: SIEMENS ADIVA 1800. Chemistry Glucose oxidase method. (Glucose (GLUO) reagent catalogue number 10492319)
HbA1C	Clinical Chemistry Analyser: SIEMENS ADIVA 1800. Chemistry A1c_E assay.

	(Glycated haemoglobin HbA1 (A1c-E) reagent catalogue number 10720857)
Insulin	Siemens Adiva Centaur assay (two site-sandwich assay). (Insulin reagent catalogue number 2230141)

(1) Methods obtained from Affinity Biomarker labs.

Urine samples

The following biomarkers in urine will be analysed in the urine.

Analyte	Analysis method
Urinary potassium	Flame photometry
Urinary sodium	Flame photometry
Urinary creatinine	Jaffe reaction via lab clinical chemistry analyser

All samples will be analysed by either the study lead or a delegated trained research student under their supervision, in the Department of Nutritional Science's main laboratory, [name].

FMD

Doppler ultrasound videos will be analysed using automated software (unnamed thus far) with our collaborators in Maastricht university, Netherlands. No laboratories will be required for their analysis.

Ideal parameters for %FMD are between 5-8%, but this can vary on the population. As there is considerable overlap between healthy and non-healthy populations (72), there are no out of range values considered in the analysis.

